4.3.4 Clinical Laboratory Tests

A Laboratory Manual will be provided to the sites that specifies the procedures for collection, processing, storage, and shipment of samples, as well as laboratory contact information, specific to this clinical research study.

Clinical laboratory safety tests including serum pregnancy tests will be performed in a licensed central clinical laboratory. Abnormal laboratory results that are considered clinically relevant by the investigator should be repeated as soon as possible (preferably within 24 to 48 hours). Subjects do not need to be fasting prior to collection of blood samples.

The following clinical laboratory tests will be performed (see Table 4.2.1-1, Table 4.2.2-1, and Table 4.2.3-1 for the schedule of tests):

Serum Chemistry

- Calcium
- Chloride
- Potassium
- Sodium •
- Bicarbonate •
- Aspartate aminotransferase (AST) •
- Alanine aminotransferase (ALT) •

- Alkaline phosphatase (ALP)
- Total bilirubin •
- Gamma glutamyl transferase (GGT)
- Creatinine
- Blood urea nitrogen (BUN)
- Glucose
- Albumin

Note for serum chemistries: Tests for AST, ALT, ALP, and total bilirubin must be conducted concurrently and assessed concurrently.

Hematology

- White blood cell (WBC) count with differential
- Red blood cell (RBC) count
- Hematocrit
- Hemoglobin •
- Platelet count

Activated partial thromboplastin time (aPTT; •

Prothrombin time (PT; screening only)

- Differential blood count •
- Mean corpuscular volume (MCV) ٠
- Mean corpuscular hemoglobin concentration (MCHC)

Urinalysis

- Color
- Appearance
- Specific gravity
- pН .
- Protein
- Glucose •
- Ketones
- Blood •

Bilirubin

Leucocyte esterase

screening only)

- Urobilinogen
- Nitrite
- Urine microscopy and urine casts (as required)
- Urine culture (as required) •
- Urine drug screen (Visits 1 and 2)

Note: Urinalysis for specific gravity, pH, protein, glucose, ketones, blood, and bilirubin may be performed at the site using a licensed test (dipstick).

Pregnancy Test (females of childbearing potential only)

Serum beta human chorionic gonadotropin (~HCG; at screening and Day -1)

Other Safety Tests

- Hepatitis B surface antigen, hepatitis C antibody (screening only)
- Human immunodeficiency virus-1, -2 (HIV-1,-2) antibody (screening only)

4.3.5 Pharmacokinetic Evaluation and Methods

Blood samples for PK will be taken immediately (within 30 minutes) prior to administration of investigational product on Day 1, at 24 hours (Day 2; \pm 30 minutes), and on Days 4, 6, 8, 10, 15, 22, 36, and 57 after dosing to determine the PK profile of tralokinumab (see Table 4.2.2-1 and Table 4.2.3-1). Tralokinumab serum concentrations will be measured by a validated immunoassay method on Gyrolab platform.

Specific procedures for sample collection, processing, storage, and shipment can be found in a separate laboratory manual provided to sites.

4.3.6 Immunogenicity Evaluation and Methods

Blood samples will be collected for the assessment of ADA against tralokinumab on Day 1 immediately (within 30 minutes) prior to administration of investigational product and on Day 57 as outlined in Table 4.2.2-1 and Table 4.2.3-1. Samples will be measured for the presence of ADA using a validated method.

4.3.7 Biomarker Evaluation and Methods

4.3.7.1 Serum Biomarkers

Blood samples will be collected for the assessment of serum biomarkers (including periostin and DPP-4) that are relevant to the mechanism of action of tralokinumab immediately (within 30 minutes) prior to administration of investigational product on Day 1, and on Days 8, 36, and 57 as outlined in Table 4.2.2-1 and Table 4.2.3-1.

4.3.8 Estimate of Volume of Blood to Be Collected

The estimated volume of blood to be collected from each subject at each visit (and across all visits) from screening through Day 57 is presented in Table 4.3.8-1. If repeats of any blood tests are required, the volume of blood collection will increase accordingly.
Visit Day	Estimated Blood Volume (mL)
Day -21 to Day -1 (Visit 1)	17
Day -1 (Visit 2)	12.5
Day 1 (Visit 2)	10
Day 2 (Visit 3)	2
Day 4 (Visit 4)	2
Day 6 (Visit 5)	2
Day 8 (Visit 6)	19.5
Day 10 (Visit 7)	2
Day 15 (Visit 8)	14.5
Day 22 (Visit 9)	2
Day 36 (Visit 10)	19.5
Day 57 (Visit 11)	22.5
Total	125.5

Table 4.3.8-1 Estimate of Blood Volume to be Collected

4.4 Study Suspension or Termination

The sponsor reserves the right to temporarily suspend or terminate this study at any time. The reasons for temporarily suspending or terminating the study may include but are not limited to the following:

- 1. The incidence or severity of AEs in this or other studies indicates a potential health hazard to subjects
- 2. Subject enrollment is unsatisfactory
- 3. Non-compliance that might significantly jeopardize the validity or integrity of the study
- 4. Sponsor decision to terminate development
- 5. Sponsor decision to terminate the study based on a planned futility analysis

If MedImmune determines that temporary suspension or termination of the study is required, MedImmune will discuss the reasons for taking such action with all participating investigators (or head of the medical institution, where applicable). When feasible, MedImmune will provide advance notice to all participating investigators (or head of the medical institution, where applicable) of the impending action.

If the study is suspended or terminated for safety reasons, MedImmune will promptly inform all investigators, heads of the medical institutions (where applicable), and/or institutions conducting the study. MedImmune will also promptly inform the relevant regulatory authorities of the suspension/termination along with the reasons for such action. Where required by applicable regulations, the investigator or head of the medical institution must inform the Institutional Review Board (IRB)/Independent Ethics Committee (IEC) promptly and provide the reason(s) for the suspension/termination. If the study is suspended for safety reasons and it is deemed appropriate by the sponsor to resume the study, approval from the relevant regulatory authorities (and IRBs/IECs when applicable) will be obtained prior to resuming the study.

4.4.1 Study-stopping Criteria

If the sponsor receives a report of an event that is consistent with any of the following study-stopping criteria, the medical monitor will immediately assess the event by gathering all available information, including, where possible, direct telephone contact with the reporter. A prompt review of the data will be initiated by the sponsor and the information will be referred to the MedImmune Safety Review Board (MSRB) within 1 business day of the receipt of the initial report by the sponsor. If an event occurs that in the opinion of the MSRB contraindicates further dosing of additional subjects, administration of tralokinumab will be stopped and no additional subjects will be enrolled into the study until further evaluation. The medical monitor will ensure that relevant safety information is distributed to MedImmune Patient Safety as appropriate. The following are criteria for stopping the study:

- 1. Death in any subject in which the cause of death is assessed as related to tralokinumab
- 2. Events that in the opinion of the medical monitor and the MSRB contraindicate further dosing of additional subjects, including anaphylaxis (as defined in Appendix 7) requiring treatment with epinephrine and assessed as related to tralokinumab

In addition, any unforeseen events that, in the opinion of the medical monitor contraindicate further dosing of additional subjects may result in interruption of the study and cessation of further dosing of tralokinumab. If the study is interrupted, a prompt cumulative review of safety data and the circumstances of the event in question will be conducted (within 7 working days) to determine if dosing should be resumed, if the study or the protocol should be modified, or if the study will be permanently discontinued. Review and approval by the MSRB will be required before the study may be resumed in the event that the study was interrupted for one of the study-stopping criteria. Where applicable, regulatory authorities and the IRB will be notified of any actions taken. Any subjects who have already received investigational product and are currently enrolled in the study at the time study-stopping criteria are met will continue to be followed by the investigator for safety.

4.5 Investigational Products

4.5.1 Identity of Investigational Product(s)

MedImmune will provide the investigator(s) with investigational product (Table 4.5-1) using designated distribution centers.

Table 4.5-1 Identification of Investigational Products

Investigational Product	Manufacturer	Concentration and Formulation as Supplied
Tralokinumab (CAT-354)	MedImmune	
w/w _ waight man waluma		

w/v = weight per volume.

Investigational product will be supplied to the site in vials with identical appearances in coded kits. Each kit has a unique number that is printed on all labels within the kit (ie, the outer carton label and the label of each vial within the carton).

4.5.1.1 Investigational Product Dose Preparation

Instructions for preparation of the investigational product are provided in Section 4.5.1.4.

4.5.1.2 Dose Calculation

No dose calculation is required for this study.

4.5.1.3 Investigational Product Inspection

Each vial selected for dose preparation should be inspected. Tralokinumab is supplied as a sterile liquid formulation at a concentration of 150 mg tralokinumab per vial (nominal in 1.0 mL) intended for parenteral administration.

If there are any defects noted with the investigational product, the investigator and site monitor should be notified immediately. Refer to the Product Complaint section for further instructions.

4.5.1.4 Dose Preparation Steps

No incompatibilities between tralokinumab and dosage administration components (ie, syringe, extension set, and SC insertion set) have been observed.

The unblinded investigational product manager will be responsible for preparing the SC doses using the steps outlined below:

- 1. All vials of investigational product **must** be equilibrated to room temperature for a minimum of 30 minutes prior to dose preparation
- The investigational dose volume plus an additional 1.5 mL of dose volume to account for losses in the administration set should be removed from the vials using a 10 mL Becton, Dickinson, and Company (BD) Luer-Lok syringe following aseptic technique (see Table 4.5.1.4-1)
- 3. It is recommended that a 19 gauge (G) $\times 1^{1/2}$ " hypodermic needle be used to withdraw the investigational product dose volume from the vials

Cohort	Total Dose Volume
1	$2 \times 2.5 \text{ mL}$
2	$1 \times 3.5 \text{ mL}$
3	1 × 3.5 mL
4	$1 \times 3.5 \text{ mL}$

Table 4.5.1.4-1 Dose Preparation Summary

Tralokinumab does not contain preservatives and any unused portion must be discarded. Preparation of investigational product syringe is to be performed aseptically. Total in-use storage time from preparation of investigational product/needle puncture of the investigational product vial to start of administration should not exceed 4 hours at room temperature or 24 hours at 2°C to 8°C (36°F to 46°F). If storage time exceeds these limits, a new dose must be prepared from new vials.

4.5.1.5 Treatment Administration

The day of dosing is considered Day 1. In each cohort, subjects will receive a single SC dose of 300 mg tralokinumab administered as 2×1 mL injections at a flow rate of 6 mL/min (for each injection; Cohort 1), or 1×2 mL injection at flow rates of 12, 2, or 0.167 mL/min (Cohorts 2, 3, or 4, respectively).

The investigational product will be administered into the abdomen via the SC route using a syringe pump (Harvard PHD Ultra infuse/withdraw [703006]). For Cohort 1, two separate injection sites will be used for each injection. The injections will be administered concurrently on the same side of the abdomen and spaced at least 3 cm apart. The time of the first SC injection for each subject in Cohort 1 will be recorded.

The fluid path consists of sterile, 510(k)-cleared components attached together via Luer-Lok connections. Specific dosage administration components include the following:

- 10 mL plastic Luer-Lok syringe (BD; 309604)
- Microbore extension set (B Braun; V6203)

- 25 G x $\frac{1}{4}$ Surflo[®] winged infusion set with 8" tubing (Tenuno; SV*25EL)
- Inset infusion system 6 mm cannula 23" tubing (Unomedical [Animas]; 100-182-00)

The BD 10 mL plastic syringe and B Braun microbore extension set will be used for all cohorts. The following SC insertion sets will be used per cohort:

- Cohorts 1 and 2: Terumo 25 G x Surflo winged infusion set with 8" tubing
- Cohorts 3 and 4: Animas Inset infusion system 6 mm cannula 23" tubing.

The fluid path should be primed using 1 mL dosing volume at an infusion rate of 2 mL/minute before administration for all cohorts.

Preparation and Administration

The following steps are to be followed in preparing the needle insertion site and administering investigational product:

- 1. The skin surface of the needle insertion site should be wiped with alcohol and allowed to air diy.
- 2. For Cohorts 1 and 2:
 - a. Pinch the skin to isolate the SC tissue from the muscle and insert the needle at a 45-degree angle.
 - b. Place a small piece of folded gauze under the winged infusion set to maintain the needle angle.
 - c. Tape the winged infusion set in place to minimize needle movement during the course of the injection.
- 3. For Cohorts 3 and 4: Follow the manufacturer's instructions for applying the Inset infusion system and insert the soft cannula at a 90-degree angle into the SC tissue.
- 4. Inject the investigational product into the SC tissue using the syringe pump at the flow rates specified for each cohort.
- 5. Keep the needle in place for **10 seconds** after the syringe pump has stopped delivering investigational product and prior to needle withdrawal.
- 6. *Do not* massage the injection site following the injection.
- 7. Some investigational product may remain in the syringe, extension set, and infusion set after the infusion is completed.
- 8. All injection-site assessments are to start after needle has been withdrawn.

If any of the following should occur, the investigator should reschedule the visit and investigational product should not be administered:

- The subject has an intercurrent illness that in the opinion of the investigator and/or medical monitor may compromise the safety of the subject in the study (eg, viral illnesses)
- The subject is febrile (≥ 38°C; ≥ 100.4°F) within 72 hours prior to investigational product administration

Injection site(s) will be assessed immediately post-injection, once the needle insertion set has been withdrawn, and at 10, 20, 30, and 60 minutes and then at 2, 4, 8, 24, and 72 hours post-injection as described in Section 4.3.3. For Cohort 1, assessments will be done after the second injection has been administered. At each time point the blinded assessor will complete the injection site assessment questionnaire; but will not complete an AE eCRF for injection-site reactions, unless the reaction meets one of the following criteria:

- Fulfils the criteria for an SAE
- Leads to premature termination of the injection during investigational product administration
- Requires concomitant medication or other medically important intervention
- Has an impact on the general condition of the subject as judged by the investigator

Injection-site reactions persisting beyond 72 hours will be followed up to resolution.

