1.6.2 Secondary Hypotheses

The secondary hypotheses to be tested are:

- 1. Increasing the volume of injection of tralokinumab from 1 mL to 2 mL reduces the tolerability of the injection at a given flow rate (as measured by pain, pruritus, and local injection site reactions)
- 2. Decreasing the flow rate of injection of tralokinumab improves the tolerability of the injection (as measured by pain, pruritus, and local injection site reactions)

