4.6 Treatment Assignment and Blinding

4.6.1 Methods for Assigning Treatment Groups

Subjects will be randomized in a 1:1:1:1 ratio to 1 of 4 cohorts to receive a single SC dose of 300 mg tralokinumab on Day 1 administered as either 2×1 mL injections at a flow rate of 6 mL/min for each injection (Cohort 1) or a 1×2 mL injection at flow rates of 12, 2, or 0.167 mL/min (Cohorts 2, 3, or 4, respectively). Randomization will be stratified by gender. A minimum of 5 males and 5 females will be randomized to each cohort; the additional subjects may be of either sex. The allocation to each cohort will be open label. Only the injection-site assessor will be blinded to treatment allocation of all subjects (except those randomized to Cohort 1 due to the requirement for 2 separate injections).

The procedure for randomization will be as follows:

- 1. On Day 1, the investigator or designee will confirm subject eligibility.
- 2. The SID number and gender will be communicated to the pharmacist/designee.
- 3. The pharmacist/designee will use a randomization list to assign a randomization number and dispense the investigational product to the subject.
- 4. The site team will record the appropriate information in the subject's medical records. The pharmacist/designee will maintain a master investigational product accountability log and batch preparation records.

Investigational product (tralokinumab) must be administered the same day the investigational product is assigned. If there is a delay in the administration of investigational product such that it will not be administered within the specified timeframe, the study monitor must be notified immediately.

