4.8.2 Sample Size and Power Calculations

The number of subjects planned for this study is based on the number required to obtain adequate PK data while exposing as few healthy volunteer subjects as possible to tralokinumab and procedures. A total of 15 subjects per treatment arm is considered sufficient to detect an approximately 1.5-fold difference in PK parameters between cohorts and will provide exploratory information regarding local tolerability.

A previous single-dose study investigating the PK of tralokinumab (Study CD-RI-CAT-354-1054) showed a coefficient of variation (CV) of 37% for area under the serum concentration-time curve from zero to infinity (AUCO-). Assuming the same CV across the cohorts and using a two-sided two-sample t-test at a significance level of 0.05, with 15 subjects per cohort the study will be 84% powered to detect a 1.5-fold difference in AUC_{0-} between Cohort 1 and any of the other treatment cohorts.

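### Flow rate is tied to the insertion set, so only Cohort 4 versus Cohort 3 supports a flow-rate conclusion for tolerability and leakage

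*Protocol*

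**What the plan says.** Section 4.5.1.5 of the protocol lists two insertion sets and allots them by cohort:

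- "Cohorts 1 and 2: Terumo 25 G x Surflo winged infusion set with" 8-inch tubing. The skin is pinched, the needle goes in at 45 degrees, and the set is taped down.
- "Cohorts 3 and 4: Animas Inset infusion system 6 mm cannula", with 23-inch tubing. Staff are to "insert the soft cannula at a 90-degree angle into the SC tissue".

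Only the syringe and the extension set are common to all four cohorts. Sections 3.1.1 and 3.1.2 mention a syringe pump and an insertion set without saying that there are two kinds, and present the three 2 mL cohorts as differing by flow rate.

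Secondary hypothesis 2 (section 1.6.2) reads "Decreasing the flow rate of injection of tralokinumab improves the tolerability of the injection", judged on pain, pruritus and local reactions. Hypothesis 1 concerns going from 1 mL to 2 mL with flow rate held fixed. Section 3.2.3 measures leakage to learn whether flow rate affects delivery of the 2 mL volume. Section 1.5 expects the study to describe how volume and flow rate relate to tolerability and PK, for use in device design and in planning later studies. The protocol gives no reason for using two sets and does not acknowledge that set and rate move together.

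**The concern.** The two fastest rates always go with the needle at 45 degrees and the two slowest always with the soft cannula at 90 degrees. No cohort crosses the two factors. Randomization ("Subjects will be randomized in a 1:1:1:1 ratio to 1 of 4 cohorts") balances the subjects, but the set is part of what is assigned, so randomization cannot separate it from the rate.

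This matters most for the local endpoints. Pain, pruritus, local reactions and leakage are all judged at the puncture made by the set, starting right after it is withdrawn. If Cohort 3 or 4 looks better than Cohort 2, the data cannot say whether the slower rate or the different set and angle was responsible. As written, the plan would let that difference be read as support for hypothesis 2 and carried into a flow-rate specification for the device.

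**Working it through.** **The plan's own figure.** Section 4.8.2 takes a previous study that "showed a coefficient of variation (CV) of 37"% for AUC to infinity and, "using a two-sided two-sample t-test at a significance level of 0.05", states that "with 15 subjects per cohort the study will be 84% powered to detect a 1.5-fold difference" between Cohort 1 and any other cohort. On the log scale:

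- SD = √ln(1 + 0.37²) = 0.358; difference = ln 1.5 = 0.405
- Noncentrality = 0.405 / (0.358 × √(2/15)) = 3.10, with 28 degrees of freedom
- Power = 84.9%, or 82.6% if 0.37 itself is used as the log-scale SD

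The stated 84% is reproduced to within 2 points. It concerns detecting a difference, not attributing one, so it is unaffected by what follows.

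**The six contrasts.** Inputs are from sections 3.1.2 and 4.5.1.5: Cohort 1 is 2 × 1 mL at 6 mL/min, needle; Cohort 2 is 1 × 2 mL at 12 mL/min, needle; Cohort 3 is 1 × 2 mL at 2 mL/min, cannula; Cohort 4 is 1 × 2 mL at 0.167 mL/min, cannula.

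| Pair | Volume and sites differ | Flow rate differs | Set and angle differ |
|---|---|---|---|
| 1v2 | yes | yes (6, 12) | no |
| 1v3 | yes | yes (6, 2) | yes |
| 1v4 | yes | yes (6, 0.167) | yes |
| 2v3 | no | yes (12, 2) | yes |
| 2v4 | no | yes (12, 0.167) | yes |
| 3v4 | no | yes (2, 0.167) | no |

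- Set and rate change together in 4 of 6 pairs. These include 2 of the 3 comparisons with Cohort 1 and 2 of the 3 comparisons among the 2 mL cohorts.
- Flow rate changes alone in 1 of 6 pairs, 3v4.
- No pair shares a flow rate, so none meets the fixed-rate condition of hypothesis 1. Cohorts 1 and 2 match on injection time (1/6 min and 2/12 min, both 10 seconds) but not on rate.

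**Can a model separate the factors?** For the 2 mL cohorts, write each cohort mean as m = a + b·ln(rate) + s·(cannula). That is three unknowns for three means. Cohort 2 is the only needle cohort, so it fixes only the needle-versus-cannula shift. The slope is then b = (m₃ − m₄) / (ln 2 − ln 0.167) = (m₃ − m₄) / 2.483, which is the 3v4 contrast and nothing else. Adding Cohort 1 adds one mean and one unknown (2 × 1 mL versus 1 × 2 mL) and leaves b unchanged. Among the 2 mL cohorts, log rate and set correlate at −0.82.

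**How much of the range remains.** The 2 mL cohorts span 12/0.167 = 71.9-fold, and 3v4 spans 2/0.167 = 12.0-fold. On the log scale that is 2.483/4.275 = 58% of the range. The other 42%, the 6-fold step from 2 to 12 mL/min, is crossed only by changing the set as well.

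**The case against.** The strongest reply has four parts.

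- **The study is exploratory.** Pain and pruritus differences are only to be explored (sections 4.8.4.2 and 4.8.4.3), and leakage has no statistical analysis (section 4.8.4.1). This lowers the stakes, but the protocol still states a directional flow-rate hypothesis and a device-design use, and descriptive summaries confound in the same way.
- **Analysis detail is deferred to the SAP**, which is not at hand. That is fair for models and tables. The set allocation and the hypotheses are fixed in the protocol, however, and the algebra above shows that no model recovers what the allocation ties together.
- **Scoring starts only after withdrawal**, apart from pain at 1 and 6 minutes in Cohort 4, so insertion pain is captured indirectly. This stands in part. In Cohort 2, though, delivery takes 10 seconds and the hold another 10, so the first score follows insertion and withdrawal closely. How far any set effect persists to 72 hours cannot be judged from the protocol.
- **Two sets may be technically necessary.** Possibly, but no reason is given, and necessity would not restore attribution.

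A reader might also infer more than the protocol supports:

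- That the primary PK comparison is invalid. It is not: section 1.6.1 compares 2 mL delivery with 2 × 1 mL delivery as regimens, and randomization supports that.
- That the set alters PK through the depth of the deposit. Nothing in the protocol allows depth, or any set effect on PK, to be derived.
- That Cohort 2 versus Cohort 1 is a clean volume contrast. The rates of 12 and 6 mL/min rule that out.
- That one common set should be used. Whether one set could serve all rates is unknown from the text, and the change would alter administration.

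**Conclusion.** The concern holds for attribution. Flow rate and insertion set cannot be separated in 1v3, 1v4, 2v3 and 2v4 at any sample size. Cohort 2 versus Cohort 1 mixes volume per injection, number of sites and rate. Only Cohort 4 versus Cohort 3 isolates flow rate. Hypothesis 2 is therefore testable, but only between 2 and 0.167 mL/min, and the same limit applies to the leakage rationale.

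The primary PK comparison with Cohort 1 and its stated power stand. The limit there is one of interpretation: a PK difference in Cohorts 3 or 4 could not be put down to flow rate alone.

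The conclusion rests on the set allocation being carried out as section 4.5.1.5 states. The saturated-model step also assumes a log-linear rate effect and no interaction between set and rate; relaxing either leaves less to estimate, not more. The size of any set effect is unknown and may be small. The point is that this design could not show it to be so.

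**What to change.** Change the wording in sections 1.6.2, 3.2.3 and 4.8:

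- Name Cohort 4 versus Cohort 3 as the only contrast that supports a flow-rate conclusion for pain, pruritus, local reactions and leakage.
- Report 2v3, 2v4, 1v3 and 1v4 as comparisons of whole delivery systems: rate plus insertion set, and for Cohort 1 also volume and number of sites.
- Report Cohort 2 versus Cohort 1 as a same-set regimen comparison, stating that flow rate also differs and that the fixed-rate condition of hypothesis 1 is not met.
- Keep the PK comparison with Cohort 1 as a regimen comparison, and state that a difference seen in Cohorts 3 or 4 will not be ascribed to flow rate alone.

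This needs no change to sample size, cohorts or procedures. The cost is a narrower flow-rate claim (2 versus 0.167 mL/min only), with nothing attributable to rate alone at the fast end.

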2.2.2 Secondary Endpoint(s)

- 1. Local injection site pain intensity and injection site pruritus post-injection
- 2. Local injection site reactions (eg, erythema, bleeding, rash, etc) post-injection
- 3. Presence of fluid leakage immediately post-injection
- 4. Incidence of TEAEs including clinically significant changes in vital signs, physical examinations, and laboratory parameters

5. Presence of ADA to tralokinumab

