3.2.3 Rationale for Endpoints

Primary Endpoint

The primary endpoint of the study is the PK of tralokinumab. Each subject will receive a single dose of 300 mg tralokinumab by one of 4 administration regimens and 57 days of follow up. Based on prior data, the maximum concentration $_{(Cmax)}$ of tralokinumab usually occurs between 2-9 days with a half-life of approximately 21 days following SC administration. Therefore, the sampling scheme will provide adequate samples for the characterization of $_{Cmax}$ and area under the serum concentration-time curve (AUC) parameters through noncompartmental analysis. The PK parameters associated with a single 2 mL injection of tralokinumab at different flow rates will be compared to those associated with 2×1 mL injections of tralokinumab to determine the feasibility of larger volume delivery and to provide information to aid in the design of the final device.

Secondary Endpoints

Injection site pain will be measured using a 100 mm visual analogue scale (VAS; see Appendix 4). Local injection-site tolerability parameters will also be measured, including injection-site itch and visual assessment of the injection site for reactions such as erythema, rash, etc. As local injection-site reactions are of specific interest, they will be recorded in detail on a dedicated and standardized injection-site questionnaire (Appendix 2) at each time point post-injection. These targeted assessment events will not require reporting as adverse events (AEs) on the AE electronic case report form (eCRF), unless they meet one or more of the following criteria:

- Fulfils the criteria for a serious adverse event (SAE)
- Leads to premature termination of the injection during investigational product administration
- Requires concomitant medication or other medically important intervention
- Has an impact on the general condition of the subject as judged by the investigator

These data will be used to determine the overall tolerability of a single 2 mL injection of tralokinumab at different flow rates to determine the feasibility of this approach compared to 2×1 mL injections and to provide information to aid in the design of the final delivery device.

The degree of fluid leakage from the injection site will be assessed immediately following all injections to determine if the flow rates affect delivery of the 2 mL injection volume.

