4.3.3.1 Investigational Product Leakage

The investigator or qualified designee will visually examine the injection site for investigational product leakage immediately following the injection, once the needle insertion set has been withdrawn, on Day 1 as outlined in Table 4.2.2-1 and Table 4.2.2-2.

If leakage is present, the injection site will be blotted with pre-weighed absorbent material and the amount of leakage will be quantified and recorded. For subjects in Cohort 1 who will receive 2×1 mL injections of tralokinumab, the overall assessment of fluid leakage from both injection sites combined should be recorded immediately post-injection.

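### Leakage weighing omits the gauze placed under the winged set in Cohorts 1 and 2, so recorded leakage could be biased low in those arms

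*Protocol*

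**What the plan says.** **Endpoint and purpose.** Protocol 2.2.2 lists as a secondary endpoint "Presence of fluid leakage immediately post-injection". Section 3.2.3 gives the reason for assessing it: "to determine if the flow rates affect delivery of the 2 mL injection volume". Section 4.8.4.1 summarizes the degree of leakage by cohort, descriptively only.

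**Measurement.** Section 4.3.3.1 has staff look for "investigational product leakage immediately following the injection, once the needle insertion set has been withdrawn, on Day 1". It continues: "If leakage is present, the injection site will be blotted with pre-weighed absorbent material and the amount of leakage will be quantified and recorded". For Cohort 1 the two sites are combined into one leakage result. Step 8 of 4.5.1.5 gives the same timing: "All injection-site assessments are to start after needle has been withdrawn". Tables 4.2.2-1 and 4.2.2-2 schedule leakage and gravimetric analysis at the immediate post-injection time point.

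**Administration, Cohorts 1 and 2.** Steps 2a to 2c of 4.5.1.5 use a winged set with the needle at 45 degrees. Step 2b reads: "Place a small piece of folded gauze under the winged infusion set to maintain the needle angle". Step 2c reads: "Tape the winged infusion set in place to minimize needle movement during the course of the injection". Step 5 then keeps the needle in for 10 seconds "after the syringe pump has stopped delivering investigational product and prior to needle withdrawal".

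**Administration, Cohorts 3 and 4.** Step 3 uses a different set, a soft cannula inserted at 90 degrees according to the manufacturer's instructions. The protocol names no gauze for these cohorts.

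**The concern.** An absorbent item lies beside the puncture site while fluid could track back, and it is outside the measurement. Two features make this more than untidy.

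First, weighing is conditional on leakage being seen on the skin. Fluid taken up by the gauze could therefore lower the recorded amount, and could also turn a subject with leakage into one recorded as having none.

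Second, the gauze follows cohort. Of the three 2 mL arms, the fastest has it and the two slower ones have none named. Any loss into gauze would make the 12 mL/min injection look less leaky than it was. Section 1.5 says the data will be used to set the design specifications of the future delivery device, so a false impression that fast delivery does not leak is the error to avoid.

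This happens at data collection. Gauze discarded unweighed on Day 1 cannot be recovered by any later analysis.

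**Working it through.** The protocol gives no leakage volume or rate, so it has no figure of its own to reproduce on this point. Its one design figure, 84% power in 4.8.2, concerns AUC. It reproduces at 82.6% to 84.9%, depending on how the CV of 37% is put on the log scale, and it does not enter here.

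**1. How long the gauze is in place.** Delivery time = volume / flow rate, with inputs from Table 3.1.2-1. The dwell is from 4.5.1.5 step 5.

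| Cohort | Delivery time | Plus 10 s dwell | Gauze named |
|---|---|---|---|
| 1 (each injection) | 1 mL / 6 mL/min = 10 s | 20 s | yes |
| 2 | 2 mL / 12 mL/min = 10 s | 20 s | yes |
| 3 | 2 mL / 2 mL/min = 60 s | 70 s | no |
| 4 | 2 mL / 0.167 mL/min = about 12 min | about 12 min 10 s | no |

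No step removes the gauze before the set, so it is under the wings for about 20 seconds of delivery and dwell at each injection.

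**2. What is counted.** Setting 4.3.3.1 beside 4.5.1.5:
- Inspection starts after withdrawal.
- Only the blotting material is described as pre-weighed.
- Blotting is done only if leakage is present.
- The gauze is mentioned once, as a support for the needle angle, with no weighing or inspection before or after use.

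Followed as written, recorded leakage = fluid still on the skin when the site is inspected. Fluid in the gauze is not part of it.

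**3. Which comparisons are touched.**
- Cohort 2 against Cohort 3 or 4 (flow rate at 2 mL): gauze on one side only.
- Cohort 1 against Cohort 3 or 4: gauze on one side only.
- Cohort 1 against Cohort 2: gauze in both, so any loss need not be equal but is not one-sided.
- Cohort 3 against Cohort 4: no gauze named in either.

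**4. Scale, as an assumption.** Concentration is 150 mg/mL (3.2.1) and the dose is 300 mg in 2 mL. Uncounted mg = volume × 150; share of dose = mg / 300.

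| Assumed uncounted volume | mg | Share of dose |
|---|---|---|
| 0.01 mL | 1.5 | 0.5% |
| 0.05 mL | 7.5 | 2.5% |
| 0.1 mL | 15 | 5% |
| 0.2 mL | 30 | 10% |

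These volumes are illustrative. The documents support none of them over zero.

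**5. Number affected.** With one gauze per injection: Cohort 1, 15 × 2 = 30; Cohort 2, 15 × 1 = 15; total 45 pieces in 30 of 60 subjects.

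**The case against.** The case on the other side is substantial.

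- **Uptake is not shown.** No text says that fluid leaks during delivery or reaches the gauze. The gauze is there to hold an angle, its contact with the puncture point is not stated, and it is in place for only about 20 seconds. That it is unweighed, and that Cohorts 3 and 4 have none, are both read from silence. This stands: a reader might infer that drug is being absorbed uncounted, but the documents support only that it could be.
- **Staff would notice wet gauze.** They may well, since it comes away with the set just before inspection. But nothing tells them to look at it, to treat it as leakage, or to weigh it. A dry skin surface with damp gauze has no defined result.
- **Leakage during the 12-minute Cohort 4 delivery is missed too.** A reader might infer that collection should run from pump start in every cohort. The documents do not support that as a defect: the endpoint, its rationale and the schedule tables all place the assessment immediately after injection. A longer window would be a different endpoint. The gauze is different, because fluid held in it is still at the site when the assessment is made.
- **The insertion sets differ anyway.** This stands in full. A 45-degree needle and a 90-degree soft cannula may leak differently at any flow rate, and weighing gauze does not change that.
- **Stakes are low.** Leakage is one of five secondary endpoints, summarized descriptively in an exploratory study. That limits the weight of the point but does not remove it, given how little the correction costs.

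**Conclusion.** The point holds as a possible measurement bias. As written, the plan can under-record both presence and amount of leakage in Cohorts 1 and 2, and it has no matching feature in Cohorts 3 and 4. The direction of the gauze effect is one-way (low, in the arms with gauze). Its size is unknown and may be nil.

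This rests on three assumptions: the gauze is not weighed or inspected under some instruction outside the protocol; Cohorts 3 and 4 use no comparable absorbent under the manufacturer's instructions; and some fluid escapes before withdrawal and reaches the gauze.

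Two stronger conclusions are not supported. A reader might infer that the primary endpoint is compromised; it is not mis-measured, because PK comes from serum concentrations, and drug that leaks is lost whether or not it is weighed. What suffers is the leakage endpoint and its use in explaining a PK difference. A reader might also infer that counting the gauze would isolate the effect of flow rate; it would not, because Cohorts 1-2 and Cohorts 3-4 use different insertion sets.

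This is a cheap improvement, not a flaw that threatens the study.

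**What to change.** In 4.5.1.5 step 2b, require the folded gauze to be pre-weighed. In 4.3.3.1, add for Cohorts 1 and 2 that the gauze is inspected and re-weighed when the set is withdrawn, that wet gauze counts as leakage present, and that its weight gain is added to that of the blotting material. For Cohort 1, sum over both injection sites, in line with the combined result already required.

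No added absorbent in Cohorts 3 and 4 is proposed. It would alter how that set is applied, might not fit the manufacturer's instructions, and would leave the device difference in place. The time of assessment also stays as it is. The report should say that leakage differences between Cohorts 1-2 and Cohorts 3-4 are confounded with the insertion set.

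Cost: one more item to weigh before and after each injection in Cohorts 1 and 2, about 45 pieces in all, plus wording in two sections. Gravimetric analysis is already scheduled on Day 1. If the gauze stays dry, the weights document that.
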